## 5.2 Treatment/Intervention Period (Day 1 of each 28 day cycle +/- 3 days, ongoing)

Patients will be seen on D1 of each cycle of rucaparib (consisting of 28 days, +/- 3 days). The following assessments will be performed at each visit:

- conduct physical exam (including vital signs, weight)
- obtain any medical history changes from prior assessment
- assess performance status (ECOG). (Appendix A)
- review concurrent medications (see Appendix B for a listing of medications with the potential for drug interactions)
- Patients who remain on treatment for >12 months can begin to have their clinic visits, safety labs (including CBC w/diff, Comp), PSA, and toxicity assessments every 3 months.

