#### **5.5 End of Treatment/Treatment Discontinuation Visit 28 days after last dose +/- 3 days)**

- Conduct physical exam (including vital signs, height/weight)
- perform laboratory tests: Complete blood count w/Diff, PSA, Comprehensive metabolic panel
- ctDNA blood collection (10ml)
- assess performance status (ECOG). (Appendix A)
- review concurrent medications
- assess AEs
- if patient is discontinuing participation in study, perform radiographic tests: CT A/P and NM Bone Scan (if these have not been performed in the prior 3 months)

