#### **5.6 Follow-up (At least every 28 days while active AEs)**

Patients will be followed every 28 days beyond the end of treatment visit if they have withdrawn from study because of AEs. Patients withdrawn from the study because of AEs will be followed until the adverse event has either resolved or stabilized. Reasons for premature withdrawal should be determined and noted. To be performed at each visit will be:

- conduct physical exam (including vital signs, height/weight)

- perform laboratory tests (CBC w/diff, Comprehensive metabolic panel) only as indicated by AEs requiring follow-up
- assess performance status (ECOG). (Appendix A)
- review concurrent medications
- reassess AEs.
- When patient will discontinuing participation in study, perform radiographic tests: CT A/P and NM Bone Scan (if these have not been performed in the prior 3 months)

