## 10.1 Study Endpoints

### 10.1.1 Analysis of the primary endpoint

The primary endpoint of this study is PSA50 response, defined as a decrease in the PSA to 50% less than the baseline PSA upon enrollment in the trial. The decrease must be confirmed by a second measurement at least 4 weeks apart. For purposes of meeting the primary endpoint, patients will be considered to have done so if they have a PSA50 response only while on therapy with rucaparib. PSA values will be measured each cycle during the trial. All patients who are administered at least one dose of rucaparib will be considered evaluable for the primary endpoint. If patients do not have follow-up PSAs after initiation rucaparib therapy due to stopping therapy for toxicity or withdrawing consent, for example, then they will be replaced.

We will estimate the PSA50 response rate, along with the exact 95% confidence interval, for the population of patients.

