#### 10.1.2.2. PSA progression-free survival (PFS)

A standard definition of PSA progression per PCWG3 will be used. PSA PFS will be defined as an increase in 25% over a nadir value, confirmed by a follow-up PSA at least 4 weeks apart. If patients are removed from study prior to PSA progression, then they will be censored at that time.

We will use the Kaplan-Meier method to estimate the median PSA PFS.

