#### *10.1.2.3. Radiographic progression-free survival (rPFS)*

Progression-free survival will be measured from the time of first dose to objective tumor progression as defined by RECIST 1.1 for progressive disease or death and summarized using a Kaplan-Meier curve. Progression will be assigned to the earliest observed time. Patients whose disease has not progressed at follow-up will be censored at the date when the last tumor assessment determined a lack of progression.

We will use the Kaplan-Meier method to estimate the median PFS.

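### PSA-PFS is censored at an undated removal from study instead of the last PSA without progression, which can lengthen the median when removal trails that PSA

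*Combined protocol and SAP*

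**What the plan says.** Section 10.1.2.2 gives the censoring rule for PSA-PFS: "If patients are removed from study prior to PSA progression, then they will be censored at that time". The synopsis repeats it. The estimate to be reported is a median: "We will use the Kaplan-Meier method to estimate the median PSA PFS". Sections 8.1.2.2 and 8.4.2 define PSA progression but give no censoring date.

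The neighbouring endpoint is handled differently. For rPFS, section 10.1.2.3 says: "Patients whose disease has not progressed at follow-up will be censored at the date when the last tumor assessment determined a lack of progression".

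PSA is scheduled as follows.
- On treatment, section 10.1.1: "PSA values will be measured each cycle during the trial". A cycle is 28 days.
- After more than 12 months on treatment, section 5.2 allows "safety labs (including CBC w/diff, Comp), PSA, and toxicity assessments every 3 months".
- At the end-of-treatment visit, 28 days after the last dose (section 5.5): "perform laboratory tests: Complete blood count w/Diff, PSA, Comprehensive metabolic panel".
- In adverse-event follow-up after that visit (section 5.6): "perform laboratory tests (CBC w/diff, Comprehensive metabolic panel) only as indicated by AEs requiring follow-up". No PSA is listed there. Footnote c of the study calendar (Table 1), however, includes PSA among the tests for every visit.

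**The concern.** PSA progression can be seen only on a day when PSA is drawn. After his last PSA a man contributes no information on this endpoint, yet the rule keeps him event-free and at risk until he is removed. If that stretch spans dates on which other men have PSA events, he adds to the denominator without being able to add to the numerator, and the estimated curve is too high.

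Removal can trail the last PSA in several ways: missed visits, a late formal withdrawal, the optional 3-monthly schedule after month 12, or removal dated at the end of adverse-event follow-up. Because the removal date is undefined, it could also be settled after the data are seen. What is at stake is the reported median PSA-PFS, a secondary estimate in a trial with no comparator arm.

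**Working it through.** **The plan's own figures.** The documents give no median, event count or power for PSA-PFS, so there is nothing to reproduce on this endpoint. The primary design does not use it and reproduces as stated. For 6/12 and 17/28, the early stopping probability at a 50% response rate is P(X ≤ 6 of 12) = 2510/4096 = 0.613 (stated 0.61). The exact type I error is 0.0815 (limit 0.1) and power is 0.902 (stated 90%).

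**Direction.** The Kaplan-Meier estimate is S(t) = Π(1 − d_j/n_j) over event times t_j ≤ t. The events d_j are the same under both rules. If every removal date is on or after the man's last PSA, then n_j(removal) ≥ n_j(last PSA) at each t_j. Each factor is then equal or larger, and so are S(t) and the median. If removal is dated before the last PSA, this argument does not apply.

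**When it matters.** Events are dated at PSA visits. If removal falls between a man's last PSA and the next scheduled one, and visits are exactly on schedule, no event time lies in the gap. No n_j changes and the median is identical. The gap must reach other men's next PSA dates before anything moves.

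**Size.** Inputs from the documents: 28 men; PSA every 28 days through cycle 13, then every 84 days; a ±3-day window. Assumptions, since the documents give none: exponential PSA progression, exponential removal for other reasons, and the lag from stopping to the recorded removal date with no PSA drawn. The lag is applied to every censored man. Entries are the mean difference in median (removal rule minus last-PSA rule, months), with the share of simulated trials whose median was identical.

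| Assumed median PSA-PFS / median time to removal (months) | Censored | No lag | 28-day lag | 84-day lag |
|---|---|---|---|---|
| 6 / 24 | 21% | 0.1 (92%) | 0.2 (73%) | 0.5 (47%) |
| 9 / 24 | 29% | 0.1 (91%) | 0.5 (71%) | 1.1 (42%) |
| 9 / 12 | 45% | 0.3 (87%) | 0.9 (59%) | 2.2 (19%) |
| 9 / 9 | 52% | 0.4 (85%) | 1.1 (56%) | 2.7 (16%) |
| 18 / 18 | 52% | 0.5 (90%) | 1.3 (73%) | 2.9 (44%) |
| 18 / 12 | 62% | 0.7 (89%) | 1.6 (74%) | 4.0 (43%) |

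With the ±3-day window removed, the no-lag difference was 0.0 months and the median was identical in 100% of trials, in both settings run (9/12 and 18/18). The removal-rule median was never below the last-PSA median in any setting. With no lag, the gap from last PSA to removal had a median of 15 to 19 days and a 90th percentile of 32 to 63 days. Fresh random numbers moved the table entries by at most 0.5 months.

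**The case against.** A reader might infer that PSA-PFS is plainly overstated by months, because men who stop for toxicity are followed without PSA and that time counts as progression-free. The documents do not support this.
- Section 5.6 describes follow-up of men who have already withdrawn because of adverse events, and section 6.4 ties removal to criteria that end treatment. On that reading censoring comes before the follow-up.
- Section 5.5 requires a PSA at the end-of-treatment visit, so a long PSA-free stretch cannot simply run from the last on-treatment cycle.
- Table 1 footnote c and section 5.6 disagree on whether PSA is drawn in follow-up, so its absence there is not settled.
- Table 1 footnote d limits post-treatment follow-up to unresolved toxicity. A long lag cannot be applied to men who leave for other reasons.

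Nor do the documents support a claim that the error always favours the drug. If removal means the last dose, censoring precedes the end-of-treatment PSA: information is lost and the upward-bias argument does not apply.

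These points stand and cut the concern down. They do not remove it. Section 5.5 asks for scans at the end-of-treatment visit only if the man is then leaving the study, and section 5.6 asks for them when he leaves during follow-up. Participation can therefore end after adverse-event follow-up, and that date could be taken as removal. Missed visits, late withdrawals and the 3-monthly schedule are further routes to a gap. No passage supplies a last-PSA rule.

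**Conclusion.** The rule is inconsistent with the rPFS rule and rests on an undefined date. When removal trails the last PSA by about a full PSA interval or more, the Kaplan-Meier median can be biased upward, never downward. When removal is dated at treatment stop and PSA is on schedule, the effect on the median is nil or negligible.

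The size rests wholly on assumed progression times, leaving rates and lags: roughly 0 to 0.7 months for on-schedule removal, 0.2 to 1.6 for a 28-day lag and 0.5 to 4.0 for an 84-day lag. The 84-day figures are an outer case, because every censored man is given the lag. An overstated median is a possibility, not something shown. The point is minor: PSA-PFS is a secondary estimate, and the two-stage design and primary analysis are unaffected.

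**What to change.** In section 10.1.2.2 and the synopsis, replace censoring at the time of removal with: *censored at the date of the last PSA measurement (including the end-of-treatment PSA) that did not meet the progression definition*. Apply the same rule to men still on study without PSA progression at the analysis, for whom section 10.1.2.2 now gives no rule. Censor men with no post-baseline PSA at day 1. This brings PSA-PFS into line with section 10.1.2.3, where men are "censored at the date when the last tumor assessment determined a lack of progression", and makes the meaning of removal irrelevant to this endpoint. Table 1 footnote c and section 5.6 should also be reconciled on whether PSA is drawn in follow-up.

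The censoring change costs a sentence or two of analysis wording and needs no new data. The downside is that the reported median may be slightly shorter. It does not cure informative censoring of men removed for clinical or radiographic progression.

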#### *10.1.2.3. Radiographic progression-free survival (rPFS)*

Progression-free survival will be measured from the time of first dose to objective tumor progression as defined by RECIST 1.1 for progressive disease or death and summarized using a Kaplan-Meier curve. Progression will be assigned to the earliest observed time. Patients whose disease has not progressed at follow-up will be censored at the date when the last tumor assessment determined a lack of progression.

We will use the Kaplan-Meier method to estimate the median PFS.

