### 3.3 Inclusion Criteria

To be included in this study, patients should meet all of the following criteria:

- Willing and able to provide written informed consent and HIPAA authorization for the release of personal health information.  
**NOTE:** HIPAA authorization may be either included in the informed consent or obtained separately.
- Males aged 18 years of age and above
- Histological or cytologic proof of adenocarcinoma of the prostate
- Pathogenic mutation in one or more homologous recombination DNA-repair genes (*BRCA1*, *BRCA2*, *ATM*, *CHEK2*, *NBN*, *BRIP1*, *RAD50*, *RAD51C*, *RAD51D*, *PALB2*, *MRE11*, *FANCA*, *FANCB*, *FANCC*, *FANCD2*, *FANCE*, *FANCF*, *FANCG*, *FANCI*, *FANCL*, *FANCM*) as documented by a clinical CLIA-grade, saliva, tissue or blood-based (i.e leukocyte DNA) genetic or molecular test (including but not limited to Invitae, Foundation One, Color Genomics, etc). Germline and/or molecular testing will not be offered as an eligibility screen.
- All patients must be ineligible for or have declined androgen deprivation therapy (ADT)-based systemic treatment, if indicated
- Absolute PSA  $\geq 2.0$  ng/ml at screening.
- Either (1) Metastatic disease as defined for one or more bone metastases confirmed by bone scintigraphy or radiographic soft tissue metastasis by CT and/or bone scan, performed within 8 weeks.. Or (2) biochemically recurrence disease as defined by a PSA  $> 0.2$  ng/ml post prostatectomy or a PSA rise of 2ng/ml or more from the nadir after radiation therapy.
- Serum testosterone  $\geq 100$  ng/dl.
- Participants must have normal organ and bone marrow function measured within 28 days prior to administration of study treatment as defined below:
  - Hemoglobin  $\geq 10.0$  g/dL with no blood transfusion in the past 28 days
  - Absolute neutrophil count (ANC)  $\geq 1.5 \times 10^9/L$
  - Platelet count  $\geq 100 \times 10^9/L$
  - Total bilirubin  $\leq 1.5 \times$  institutional upper limit of normal (ULN)
  - Aspartate aminotransferase (AST), Alanine aminotransferase (ALT)  $< 3.0 \times$  institutional upper limit of normal

Note: Patients with elevations in bilirubin, AST, or ALT should be thoroughly evaluated for the etiology of this abnormality prior to entry and patients with evidence of viral infection should be excluded.

- Participants must have creatinine clearance estimated using the Cockcroft-Gault equation of  $\geq 51$  mL/min:

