## 5. TREATMENT/INTERVENTION PLAN

The following assessments and procedures will occur during the study. A schedule of assessments is provided in Table 1.

	Pre-study	Study Period				Off Treatment / Follow-up
		On Treatment Assessments (Every 28 days) 				
	Day -7 a, h ( $\pm 7$ days)	C1D1 h ( $\pm 3$ d)	C2D1 h ( $\pm 3$ d)	C3D1 h ( $\pm 3$ d)	CnD1 h ( $\pm 3$ d)	
Informed consent	X					
Demographics	X					
Medical history	X					
EKG	X					
Focused Medical history		X	X	X	X	X
Physical exam	X	X	X	X	X	X
Vital signs (P, BP, RR, T)	X	X	X	X	X	X
Height	X					
Weight	X	X	X	X	X	X
Performance status	X		X	X	X	X
Toxicity assessment	X		X	X	X	X
Concomitant meds	X	X	X	X	X	X
Metastatic tumor biopsy	X e				(X) e	
ctDNA (10ml)		X g				X g
Radiologic tests b	X				X b	X b
Laboratory tests c	X	X f	X	X	X	X
Rucaparib		X	X	X	X	
Adverse events			X	X	X	X

Table 1 Study Calendar

Abbreviations: CBC, complete blood count; CT, computerized tomography; MRI, magnetic resonance imaging; PSA, prostate-specific antigen

a Informed consent and radiologic assessments should be obtained within 8 weeks of study start date. EKG should be obtained within 28 days of study start date.

b Radiographic evaluations (CT A/P and NM Bone Scan) every 3 months (if metastatic disease) or every 6 months (for BCR) while enrolled in the study). They are needed within 8 weeks of screening; if previously performed then they are to be performed at screening. CT A/P and NM Bone Scan are to be performed at off-treatment visit if they have not been performed in the prior month.

c CBC w/diff, Complete Metabolic Panel, PSA, lipid panel at each visit. Testosterone, PT/INR, PTT, and Urinalysis at screening visit only and should be obtained within 28 days of study start date.

d Subjects will be followed after completion of rucaparib therapy monthly until toxicities resolve to grade 0-1. No post treatment follow up visit needed otherwise.

e Only for patients with metastatic disease: MANDATORY soft tissue Core tumor biopsy performed pretreatment (Day -7 +/- 7 days), bone biopsies are optional at pretreatment. OPTIONAL soft tissue and bone tumor biopsy on C4D1 (+/- 7 days)

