### 5.2.1 *Clinical and laboratory assessments*

On Day 1 of each cycle, patients will have a non-fasting blood drawn for the following values: Repeat labs are not needed on C1D1 as long as visit is within 7 days of screening values.

- CBC
- Comprehensive chemistry panel
- PSA
- Lipid panel
- ctDNA blood collection (10ml) (C1D1 only)

Every 3 cycles for patients with metastatic disease or every 6 cycles for patients with BCR, patients will have radiographic studies:

- CT Abdomen and Pelvis with contrast
- NM Bone scan

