**8.2.5 Bone lesions**

When the bone scan is the sole indicator of progression, disease progression in bone is defined as 2 or more new lesions seen on bone scan compared with a prior scan for used trial entry. In situations where scan findings suggest a flare reaction or where new lesion(s) may represent trauma, confirm these results with other imaging modalities (eg, MRI or fine-cut CT). If many new areas of uptake are observed, confirmation is generally not necessary.

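### Section 10.1.2.3 plans one pooled median rPFS over metastatic and BCR men, so the figure depends on an uncontrolled case mix and, to a smaller degree, on unequal scan intervals

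*Combined protocol and SAP*

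**What the plan says.** - **Estimator (10.1.2.3).** "We will use the Kaplan-Meier method to estimate the median PFS". Event dating: "Progression will be assigned to the earliest observed time". Men without progression are censored at their last tumour assessment. No stratification by disease state and no method for interval-censored data is given; the Synopsis is the same in this respect.
- **Scan intervals.** Table 1, footnote b: "every 3 months (if metastatic disease) or every 6 months (for BCR) while enrolled in the study". Section 5.2.1 states this in cycles: "Every 3 cycles for patients with metastatic disease or every 6 cycles for patients with BCR, patients will have radiographic studies".
- **Who is in rPFS.** Section 8.1.2.4 limits objective response rate to metastatic disease. Section 8.1.2.3, directly above it, puts no such limit on rPFS.
- **Case mix.** Sections 3.1 and 3.2 admit both disease states, 30 men in all. The only caps (Synopsis, 3.2, section 10) concern gene type.
- **Event definition.** Section 10.1.2.3 uses "objective tumor progression as defined by RECIST 1.1 for progressive disease or death". Section 8.1.2.3 adds PCWG3 bone-scan progression and clinical events.
- **Bone lesions.** Section 8.2.5, for the case where the bone scan is the only sign: "disease progression in bone is defined as 2 or more new lesions seen on bone scan". Section 8.4.3 also asks for at least two, and two further lesions for confirmation. Section 8.2.7, Table 5 and Table 6 count any new lesion. At entry, section 3.3 is satisfied by a single one: "Metastatic disease as defined for one or more bone metastases confirmed by bone scintigraphy".

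**The concern.** A Kaplan-Meier median summarises one population observed in one way. Here it would cover two. A metastatic man has an event when known disease worsens or spreads; a BCR man has one when disease first becomes visible on imaging. These need not occur at the same pace. Progression is dated at the scan that shows it, and BCR men are scanned half as often, so the same underlying course can be dated up to 3 months later in a BCR man.

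In a single-arm trial the rPFS median has no internal comparator. A reader will set it beside results for metastatic or BCR disease and cannot do so properly if it is a blend in unplanned proportions. A high or low figure could reflect recruitment rather than the drug.

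The bone definitions add a second uncertainty. One bone metastasis makes a man metastatic at entry, but the sections disagree on whether one new bone lesion on study is progression. Two analysts following different sections could give different event dates for the same man.

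**Working it through.** **Plan's own figure.** The documents give no assumed median, event count or precision for rPFS, so there is nothing to reproduce. True medians, BCR share and the behaviour of solitary bone lesions below are assumptions.

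**Model.** Exponential progression, F(t) = 1 − 2^(−t/m), with m the true median in months. Each event is dated at the next scheduled scan (3-month grid for metastatic men, 6-month grid for BCR men), with no censoring. The reported median is the first time the Kaplan-Meier curve is at or below 0.5.

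**1. Schedule only, equal true medians, large sample.** Let w be the BCR share. At month 9, metastatic men have been counted up to month 9 but BCR men only up to month 6. The pooled median stays at 9 while

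(1 − w)·F(9) + w·F(6) ≥ 0.5, that is, w ≤ [F(9) − 0.5] / [F(9) − F(6)].

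For m = 8: F(9) = 0.541 and F(6) = 0.405, so w ≤ 0.0415/0.1361 = 0.30. For m = 13 the same formula applies with months 15 and 12.

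| True median | All 3-month | All 6-month | Pooled median moves only above BCR share |
|---|---|---|---|
| 6.5 | 9 | 12 | 81% |
| 7 | 9 | 12 | 63% |
| 8 | 9 | 12 | 30% |
| 13 | 15 | 18 | 65% |
| 5 | 6 | 6 | never |
| 10 | 12 | 12 | never |

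The large-sample shift is therefore 0 or 3 months. At a 50/50 mix, of the four true medians that can shift (6.5, 7, 8, 13), only 8 does.

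**2. Schedule only, n = 30** (20,000 simulated trials). Average reported median at a 50/50 mix, against a common 3-month grid:

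| True median | Common 3-month | Planned 3/6-month | Difference |
|---|---|---|---|
| 5 | 6.44 | 6.70 | 0.26 |
| 8 | 9.36 | 10.23 | 0.87 |
| 14 | 15.24 | 16.01 | 0.77 |

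At a true median of 8, going from no BCR men to all BCR men moves the average from 9.4 to 11.1 months, a difference of about 1.7.

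**3. Case mix, n = 30**, assumed true medians 8 (metastatic) and 16 (BCR):

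| BCR share | Planned 3/6-month | Common 3-month |
|---|---|---|
| 0% | 9.4 | 9.4 |
| 33% | 11.7 | 11.2 |
| 50% | 13.1 | 12.4 |
| 67% | 14.7 | 13.8 |
| 100% | 18.7 | 17.2 |

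The range is 18.7 − 9.4 = 9.3 months as planned and 17.2 − 9.4 = 7.8 months on a common grid. Most of the movement is case mix, and equal scanning would not remove it. Separate reporting would.

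**4. Bone definition.** The sections side by side:

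| Source | One new bone lesion an event? |
|---|---|
| 8.2.5 | No, if the bone scan is the sole indicator |
| 8.4.3 | No |
| 8.1.2.3 | Refers to PCWG3 bone criteria, which the protocol spells out in 8.4.3 |
| 8.2.7, Table 5, Table 6 | Yes |
| 10.1.2.3 | Yes, through RECIST 1.1 alone |

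For scale, assume true medians 8 (metastatic) and 14 (BCR), 20 to 40% of BCR first progressions being one bone lesion, and a median of 6 to 12 months to a second. Requiring two lesions moves the average BCR median from 16.7 to 18.6–22.9 months and the 50/50 pooled median from 12.5 to 13.2–14.5. This run delayed BCR men only; the rule as written covers metastatic men too.

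**The case against.** **Low stakes.** rPFS is a descriptive secondary estimate with no hypothesis, and the two-stage PSA50 rule does not use it. This stands and limits the severity. Section 10.2.1 also permits subset analyses, but it does not name disease state and bars subsets as a basis for efficacy conclusions, so it does not supply the missing split.

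**The schedule effect is easily overstated.** A reader might infer that unequal scanning adds 3 months to the median. That is the contrast between an all-metastatic and an all-BCR cohort at certain true medians; it is not the effect on a pooled median at a moderate mix.

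**The model is simpler than the trial.** Treatment also ends on PSA criteria (Synopsis, 6.4). A scan is then done off schedule if none is recent (Table 1 footnote b; 5.5), and a man without radiographic progression is censored at his last assessment. Deaths and clinical events are not tied to the scan grid. This stands: the figures show direction and rough size and are not forecasts.

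**Slower progression in BCR is assumed.** The documents give no rPFS figure for either group. This stands; with equal true medians only the schedule effect remains.

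**The bone rule.** A reader might infer that the plan ignores a BCR man's first single bone metastasis. The documents do not support that as a flat statement: the analysis section relies on RECIST 1.1, under which one unequivocal new lesion counts, and 8.2.5 applies only when the bone scan is the sole sign. What they show is a conflict, and it affects metastatic and BCR men alike.

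**Conclusion.** The point holds as a moderate one, worth fixing but not critical. The plan reports one median over two disease states with different events, different scan intervals and an unplanned mix. Case mix is the larger driver: about 9 to 19 months across the full range of BCR share, if the true medians are 8 and 16. The schedule is a smaller and variable one: under about 1 month on average for 30 men at a 50/50 mix with equal true medians, and 0 to 3 months in large samples. Both results assume exponential progression, fixed scan grids and no censoring.

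It would go too far to call the pooled median meaningless. It also reflects true progression, but it cannot be interpreted without knowing the mix. Nor do the documents justify replacing the BCR endpoint with metastasis-free survival under a one-lesion rule. That would change a protocol secondary endpoint, drop its clinical-progression component, and settle by choice a question on which the sections disagree.

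**What to change.** 1. In 10.1.2.3 and the Synopsis, pre-specify Kaplan-Meier rPFS separately for mHSPC and BCR as the reported estimates, each with its number of men and events.
2. If a pooled curve is also shown, state the case mix beside it and estimate it with an interval-censored method (Turnbull), using the last negative and first positive scan dates.
3. Reconcile 8.1.2.3, 8.2.5, 8.2.7, Tables 5 and 6, 8.4.3 and 10.1.2.3, so that it is clear whether a single new bone lesion is an rPFS event. Section 3.3 should be considered at the same time, since it treats one bone metastasis as metastatic disease at entry. Because radiographic progression also takes a man off study (6.4), the protocol team must settle the definition; this review does not propose which rule to adopt.

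Cost: items 1 and 2 are SAP wording and use disease state and scan dates already collected. Item 3 needs a protocol clarification. The price is smaller groups and wider intervals, and with 30 men one of the two medians may be imprecise or not reached.
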